5.8 Safety Assessments

5.8.1 Physical Examination

Physical examinations are to be completed by the investigator or designated participating physician as indicated in the schedule of assessments (Table 10). The minimum body systems to be examined for any abnormalities and symptoms include: general appearance; skin; lymphatic;

Confidential Page 55 of 78

head, eyes, ears, nose, throat; extremities; respiratory; cardiovascular; abdominal; musculoskeletal; and neurological.

5.8.2 Vital Signs

Vital signs will be measured at all visits indicated in the schedule of assessments (Table 10) and documented in the medical record. Measurements to be reported are temperature in Celsius or Fahrenheit, pulse (beats per minute), respiratory rate (breaths per minute), oxygen saturation, and blood pressure.

Vital sign measurements will be collected within 30 minutes prior to study drug administration, and every 30 (\pm 10) minutes during the 60-minute AGEN1884 infusion, including at the end of the 15-minute flush of the infusion line (\pm 15 minutes). This would equate to 4 sets of vitals over the course of a 60-minute infusion and flush, including the pre-administration vitals. A final set of vitals will be collected 1 hour (\pm 15 minutes) following the flush of the infusion line, unless otherwise indicated.

Because AGEN1884 is administered based on subject body weight, weight will be collected before each dose of AGEN1884 to confirm the administered dose. The subject's weight at the Week 1 (Cycle 1, Day 1) visit should be used for dosing calculations unless there is a >10% change in body weight. Dose adjustments for each cycle are only needed for a >10% change in weight.

5.8.3 12-Lead Electrocardiogram

A 12-lead ECG will be recorded as indicated in the schedule of assessments (Table 10). The corrected QT (QTc) interval will be calculated using Fridericia's formula.

5.8.4 Clinical Laboratory Assessments

Blood samples will be collected and submitted to the institution's local laboratory according to the institution's standard procedures.

Standard laboratory procedures and institutional guidelines will be followed to analyze and report findings for hematology, coagulation times, and serum biochemistry.

Normal ranges with the units of measure for all required parameters will be provided to the study sponsor by the local laboratory conducting the clinical laboratory analysis. All results may be reported in conventional units if this is the typical clinic report method for the local laboratory; otherwise, the International System of units may be used.

A listing of clinical laboratory assessments to be performed is provided in Table 12.

Confidential Page 56 of 78

Table 12: Clinical Laboratory Assessments

Hematology	Red blood cell count Platelets Hematocrit Hemoglobin WBC count	WBC differentials and absolute counts: Neutrophils Eosinophils Basophils Lymphocytes Monocytes				
Serum biochemistry	Albumin Alkaline phosphatase Aspartate amino transferase Alanine amino transferase Total bilirubin Blood urea nitrogen Glucose	Creatinine Potassium Sodium Lactate dehydrogenase				
Endocrine function tests	Free thyroxine (T4) Thyroid-stimulating hormone Adrenocorticotropic hormone					
Urinalysis	Red blood cells WBCs Protein					
Coagulation	Prothrombin time INR Partial thromboplastin time					
Tumor markers	Tumors with known markers, such as alpha-fetoprotein for HCC and cancer antigen 125 for ovarian cancer					
Other	Serum and urine pregnancy tests (for women of childbearing potential only) PGx					

HCC: hepatocellular carcinoma; INR: International Normalized Ratio; PGx: pharmacogenomics; WBC: white blood cell.

5.8.5 Concomitant Medications

Concomitant medications will be recorded from date of signing of the informed consent through 90 days after the last study drug administration.

5.8.6 Adverse Events

5.8.6.1 Definitions

5.8.6.1.1 Adverse Event

An AE is defined as any untoward medical occurrence in a clinical investigation subject administered a pharmaceutical product and that does not necessarily have a causal relationship with this treatment. An AE can therefore be any unfavorable and unintended sign (including an abnormal laboratory finding that is deemed clinically significant), symptom, or disease temporally associated with the use of a medicinal (investigational) product, whether or not related to the medicinal (investigational) product.

Confidential Page 57 of 78

Examples include:

- Any clinically significant worsening of a pre-existing condition (e.g., an increase in severity or frequency of pre-existing abnormality or disorder).
- Any illness, injury, or accident, including those that appear unrelated to study treatment.
- Extensions or exacerbations or symptomatology.
- Clinically significant abnormalities in clinical laboratory, physiological testing, or physical examination.

5.8.6.1.2 Immune-Related Adverse Events

Blocking CTLA-4 function may permit the emergence of immune-mediated AEs that result in clinical syndromes resembling autoimmunity. Rash/vitiligo, diarrhea/colitis, uveitis/episcleritis, hepatitis, and hypopituitarism were drug-related, presumptive immune-related events noted in previous studies of anti–CTLA-4 agents.

For the purposes of this study, an irAE is defined as an adverse event of unknown etiology, associated with drug exposure, and is consistent with an immune phenomenon. Efforts should be made to rule out neoplastic, infectious, metabolic, toxin, or other etiologic causes prior to labeling an adverse event an irAE. Serological, immunological, and histological (biopsy) data should be used to support the diagnosis of an immune-mediated toxicity.

5.8.6.1.3 Adverse Drug Reaction

An ADR is defined as all noxious and unintended responses to a medicinal product, related to any dose. A causal relationship between the medicinal product and an AE is at least a reasonable possibility, i.e., the relationship cannot be ruled out.

5.8.6.1.4 Unexpected Adverse Drug Reaction

An unexpected ADR is an ADR whose nature or severity is not consistent with the applicable product information (e.g., Investigator Brochure). The ADRs that are more specific or more severe than described in the Investigator Brochure should also be considered unexpected.

5.8.6.1.5 Serious Adverse Event

An SAE in a clinical trial is defined as any untoward medical occurrence that at any dose, in the view of either the investigator or sponsor:

- Results in death.
- Is life-threatening (the subject was at risk of death at the time of the event; it does not refer to an event that hypothetically might have caused death if it were more severe).
- Requires in-patient hospitalization or prolongation of existing hospitalization.
- Results in persistent or significant incapacity or substantial disruption of the ability to conduct normal life functions.
- Is a congenital anomaly/birth defect.
- Any event that does not meet the above criteria, but when based on appropriate medical judgment, may require medical or surgical intervention to prevent one of the outcomes listed above, e.g., allergic bronchospasm requiring intensive treatment in an emergency room or at home; blood dyscrasias or convulsions that do not result in in-patient hospitalization; development of drug abuse or drug dependency.

Confidential Page 58 of 78

5.8.6.2 Recording and Reporting

5.8.6.2.1 Adverse Events

Subjects will be assessed for any AEs (non-serious or serious) from the date of consent until 90 days after the last study treatment. Any non-serious AEs identified during this time period will be followed until resolution or stabilization or only until the discontinuation from the study evaluation period if the event is not resolved at the conclusion of the study. The dates of onset and resolution for each AE will be recorded in the subject file. All AEs will be evaluated for duration, intensity, and attribution (relationship) to the investigational agent(s). All AEs (serious and non-serious) and laboratory abnormalities should be assessed for significance by the investigator, with consideration for the subject's overall medical history and concomitant medication profile.

If there is a change from baseline in a laboratory value, physical examination finding, vital sign, or medical finding, and the change is considered by the investigator to be clinically significant, the event must be recorded as an AE.

All AEs regardless of causality or seriousness must be recorded on the electronic case report form (eCRF). The frequency, grade, and nature of irAEs must be recorded.

5.8.6.2.2 Serious Adverse Events

All AEs that meet the SAE criteria, occurring from the date of consent, must be recorded on the AE pages of the eCRF and reported by facsimile to Agenus/PrimeVigilance within 24 hours of obtaining knowledge of the event. The facsimile report should include all available information requested on the SAE Report Form.

Email:	
Facsimile:	

The SAE Report Form will include data surrounding the event, e.g., the nature of the symptom(s), time of onset in relation to initiation of therapy, duration, intensity, and whether or not therapy was interrupted or discontinued. The investigator's assessment of the probable cause of the event will also be included. In addition, relevant medical history, concomitant medications, laboratory and diagnostic tests reports, and procedures, as well as all pertinent medical information related to the event, will also be collected.

PrimeVigilance will forward SAE queries directly to the investigator requesting incomplete or missing information. It is the investigator's responsibility to be diligent in providing this information back to PrimeVigilance as soon as it is available. Initial reports of SAEs should never be left on telephone voicemails. Always fax SAE Report Forms and follow up with a telephone call if needed.

If you have any safety-related questions or need to report an SAE, please email:

For reported deaths, the investigator should supply the sponsor and the Institutional Review Board (IRB)/Independent Ethics Committee (IEC) with any additional requested information (e.g., autopsy results, hospital discharge reports, and/or certificates of death) and should be sent as soon as they become available. Any additional information, if collected, will be reported to the sponsor as a follow-up to the initial report.

Confidential Page 59 of 78

All SAEs will be followed until the event has resolved or stabilized, regardless of causality.

It is the responsibility of the principal investigator to report SAEs to their IRB. The investigator should also comply with the applicable regulatory requirement(s) related to the reporting of unexpected serious ADRs to the regulatory authority(ies) and the IRB/IEC.

Deaths occurring during the AE reportable time frame should be reported as SAEs and recorded on the eCRF. The underlying event that resulted in death should be recorded as the verbatim term, with "death" recorded as the outcome of the event.

5.8.6.3 Adverse Events of Special Interest

In the event of a non-serious adverse events of special interest (AESI), the investigator must complete the AESI report form and send it to the Sponsor/designee immediately, within 24 hours. Names, addresses, and telephone and fax numbers for AESI reporting will be included on the report form. Serious AESIs must be reported in an expedited manner as SAEs, as outlined above.

5.8.6.4 Severity of Adverse Events

Each AE is to be classified and graded according to NCI CTCAE Version 5, publication date 27 November 2017

(https://ctep.cancer.gov/protocolDevelopment/electronic_applications/docs/CTCAE_v5_Quick_Reference 8.5x11.pdf).

If no CTCAE grading is applicable, the severity of an AE is graded as follows:

- Mild (grade 1): The event causes discomfort without disruption of normal daily activities.
- Moderate (grade 2): The event causes discomfort that affects normal daily activities.
- Severe (grade 3): The event makes the subject unable to perform normal daily activities or significantly affects his/her clinical status.
- **Potentially life-threatening/life-threatening (grade 4)**: An SAE Report Form must be completed for each grade 4 AE.
- An event that results in death is considered a grade 5 AE, meets the definition of an SAE, and must have an SAE Report Form completed for the event.

Note: All subjects who have a grade 3 or 4 AE may be considered for discontinuation from treatment by the principal investigator and after consultation with the medical monitor.

5.9 Relationship to Study Treatment

The relationship of an AE to the investigational agent will be recorded on eCRF and defined as "unrelated," "unlikely," "possible," "probable," or "highly probable/definite."

- **Unrelated**: The event is definitely not associated with study drug administration, but is judged clearly and incontrovertibly due to causes other than the study drug.
- Unlikely: An event that follows such a temporal sequence from administration of the study drug that a relationship is not likely, and is likely to be due to cause such as (known characteristics of) the subject's clinical state or other treatment.

Confidential Page 60 of 78

- **Possible**: An event that follows a reasonable temporal sequence from administration of the study drug, but that may be due to another cause.
- **Probable**: An event that follows a reasonable temporal sequence from administration of the study drug, and that is not easily explained by another cause such as known characteristics of the subject's clinical state or other treatment.
- **Highly probable/definite**: An event that follows an established temporal sequence from administration of the study drug, the re-challenge is positive, or there is a reoccurring pattern of characteristics during onset and cessation of event.

5.10 Pregnancy

Pregnancy, in and of itself, is not regarded as an AE unless there is suspicion that study drug may have interfered with the effectiveness of a contraceptive medication or method. When a pregnancy has been confirmed in a subject during maternal or paternal exposure to study drug, within 90 days of the last dose of study drug, the following procedures should be followed in order to ensure subject safety:

- The study drug must be discontinued immediately (female subjects only).
- The investigator must complete and submit the Agenus Clinical Trial Pregnancy form to the sponsor or its designee within **24 hours** of learning of the pregnancy.
- A serum pregnancy test must be performed to confirm the urine pregnancy test result. If a negative serum test does not confirm the urine pregnancy test result, then:
 - O The investigator will use his or her expert judgment, based on an assessment of the potential benefit/risk to the subject, to determine whether it is in the subject's best interest to resume study drug and continue participation in the study.
 - o The final safety visit evaluations must be performed.

Data on fetal outcome and breastfeeding are collected for regulatory reporting and drug safety evaluation. Follow-up should be conducted for each pregnancy to determine outcome, including spontaneous or voluntary termination, details of the birth, and the presence or absence of any birth defects, congenital abnormalities, or maternal and/or newborn complications, by following until the first well-baby visit. Pregnancy should be recorded on a Clinical Trial Pregnancy form and reported by the investigator to the sponsor or its designee. Pregnancy follow-up information should be recorded on the same form and should include an assessment of the possible causal relationship to the sponsor's study drug to any pregnancy outcome, as well as follow-up to the first well-baby visit or the duration specified in local regulations, whichever is later. Refer to the Agenus Study Operational Guide for Completing the Clinical Trial Pregnancy Form.

Note: Any SAE occurring during pregnancy must be recorded on the SAE report form and submitted to the sponsor or designee.

5.11 Disease Progression or Secondary Cancer or Death

For the purpose of this protocol, disease progression events should not be reported as a nonserious AE or SAE unless the criteria for an SAE are met (Section 5.8.6.1.5). If the event meets SAE criteria, a specific verbatim SAE term is to be reported (e.g., brain metastases). Details of how the event manifested should be provided in a narrative format and submitted with

Confidential Page 61 of 78

the Agenus SAE Report Form. An appropriate verbatim term that describes the subject diagnosis should be provided in the Agenus SAE Report form. The verbatim terms "disease progression" or "disease recurrence" should be avoided; if used, it will be queried for a request for an appropriate term with supportive details for the event.

Changes in any medical condition of a subject, including the diagnosis of a secondary cancer or a clinically significant change of medical status, should be reported as an AE on the appropriate eCRF and should be reported as an SAE only if the event meets SAE criteria.

Deaths occurring during the AE reportable time frame (within 90 days of study drug) should be reported as SAEs and recorded on the Agenus SAE Report Form. The underlying event that resulted in death should be recorded as the verbatim term, with "death" recorded as the outcome of the event.

6. Statistical Considerations

This section outlines the core elements of the planned statistical summaries and analyses for the data collected in this study. Detailed methodology for summary and statistical analyses of the data collected in this study will be documented in a statistical analysis plan (SAP), which will be maintained by the sponsor. The SAP may modify the plans outlined in the protocol; however, any major modifications of the primary endpoint definition and/or its analysis will also be reflected in a protocol amendment. If, after the data are locked, changes are made to the SAP, then these deviations to the plan will be documented, in the clinical study report.

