6.4 Analysis Methods

6.4.1 Safety Analysis

Descriptive statistics of safety parameters will be provided in the full safety analysis set, by dose level, and study cohort. Safety parameters include the following:

Confidential Page 63 of 78

- AEs (all AEs and irAEs, subsets of related, serious, severe, and fatal events). In addition, the number and percentage of subjects who discontinue treatment due to an AE will be provided, together with the number and percentage of subjects who die due to an AE.
- Laboratory evaluations.
- Vital signs.

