- Other AEs of special interest determined by investigators

Unless otherwise stated, the number of subjects with an event (subject-wise) and the number of events (event-wise) will be provided for each summary.

Immune-related AEs will be tabulated using investigator-reported irAEs.

Confidential Page 21 of 30

Agenus Inc. Statistical Analysis Plan for Study C-500-01 Phase 2

Infusion related AEs will be tabulated using infusion-related reactions as reported by the investigators.

The following summaries by either SOC and PT or by PT and by severity grade will be provided. Summaries will be sorted by decreasing incidence of PT (within SOC, if applicable).

- TEAEs by SOC and PT, and by PT
- TEAEs by relationship to study drug, severity grade, SOC, and PT
- Drug-related TEAEs by SOC and PT, and by PT
- TEAEs leading to permanent treatment discontinuation by PT
- TEAEs leading to death by PT
- Drug-related TEAEs leading to permanent treatment discontinuation by PT
- Drug-related TEAEs leading to death by PT
- Serious TEAEs by SOC and PT, and by PT
- Serious TEAEs by relationship to study drug and severity grade, by SOC and PT
- Drug related serious TEAEs by SOC and PT, and by PT
- irAEs by SOC and PT, and by PT
- irAEs by severity grade, SOC, and PT
- Infusion-related TEAEs by SOC and PT, and by PT
- Infusion-related TEAEs by severity grade, SOC, and PT
- Laboratory abnormalities worsening (in at least one on-study measurement, relative to baseline) by NCI-CTCAE version 5 criteria.
- Alanine aminotransferase (ALT), aspartate aminotransferase (AST), or bilirubin normal at baseline but with elevations $\geq 2 \times \text{upper limit of normal (ULN)}$

The overall summary of TEAEs will be reported by age (age < 55 vs age \geq 55, age < 65 vs age \geq 65, and age < 75 vs age \geq 75), by race group including at least 5 subjects (groups with < 5 subjects will be reported summarily as "Other"), by normal vs abnormal creatinine and bilirubin levels at baseline, and by drug manufacturing process. Subgroup analyses will be provided for HCC patients, non-HCC and PD-1/PD-L1 refractory patients, and non-HCC and PD-1/PD-L1 naïve patients.

In addition, the overall summary of AE incidence per month of drug exposure will be presented. Such a summary will report #patients/(total time of exposure in months) and #AEs/(total time of exposure in months.)

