The analysis of irAEs in the above summaries will be performed using data as reported by investigators (the primary analysis). In addition, as an exploratory analysis, TEAEs using sponsor's definition of irAEs, will be summarized. If an AE falls within any of the cluster terms listed below, it will be considered as an irAE by sponsor's definition. For each irAE, the summary will include median time (and range) to onset, median duration (and range) in days of

Confidential Page 22 of 30

the first instance of such AE per patient. Finally, descriptive statistics will be provided for time of onset, cycle of onset, and cumulative dose at onset of first irAE by SOC.

If an SOC or PT was reported more than once for a subject, the subject would only be counted once in the incidence for that SOC or PT.

In tabulation by severity grade:

- For a given SOC, only the most severe SOC for each subject will be included
- For a given PT, only the most severe PT for each subject will be included

In addition, TEAEs (evaluated within the extended treatment period) will be reported for the following clusters of immune-mediated AEs: pneumonitis, colitis, diarrhea, hepatitis, hypothyroidism, hyperthyroidism, thyroiditis, hypophysitis, adrenal insufficiency, diabetes, nephritis, rash, pruritus, and other immune-related AEs. These clusters will be defined by the following MedDRA version 22.1 Preferred Terms:

- **Pneumonitis**: interstitial lung disease; pneumonitis; acute interstitial pneumonitis; immune-mediated pneumonitis
- Colitis: allergic colitis, autoimmune colitis, colitis, colitis erosive, colitis microscopic, enterocolitis hemorrhagic, eosinophilic colitis, necrotizing colitis, neutropenic colitis, enterocolitis, immune-mediated enterocolitis,
- Diarrhea: diarrhoea, diarrhoea hemorrhagic
- **Hepatitis:** acute hepatic failure, autoimmune hepatitis, hepatic failure, hepatitis, hepatitis acute, hepatoxicity, liver injury, hepatocellular injury, immune-mediated hepatitis, immune-mediated hepatic disorder, drug-induced liver injury
- **Hypothyroidism:** autoimmune hypothyroidism, hypothyroid goiter, hypothyroidism, immune-mediated hypothyroidism, myxoedema, thyroid atrophy
- **Hyperthyroidism**: Basedow's disease, hyperthyroidism, Marine Lenhart syndrome, primary hyperthyroidism, immune-mediated hyperthyroidism, secondary hyperthyroidism, tertiary hyperthyroidism, thyroid dermatopathy, thyroid crisis, thyrotoxic periodic paralysis, toxic goiter, toxic nodular goiter,

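### The SAP's immune-mediated clusters select by preferred term alone, so liver failure or encephalopathy from tumour or liver disease can be counted as immune toxicity even when judged unrelated

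*Protocol*

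**What the plan says.** Three pieces of text meet here.

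**Recording (Protocol 5.11).** Progression stays out of AE reporting as a rule: "disease progression events should not be reported as a nonserious AE or SAE unless the criteria for an SAE are met". Once it is serious, the instruction is "If the event meets SAE criteria, a specific verbatim SAE term is to be reported (e.g., brain metastases"). Sites are told to avoid the bare terms for progression or recurrence, which will be queried, and to give a term that fits the subject's diagnosis. A death within 90 days of study drug is reported as an SAE under the event that led to it.

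**Definition (Protocol 5.8.6.1.2).** For this study an irAE is an event of unknown etiology that is associated with drug exposure and fits an immune mechanism. The section adds: "Efforts should be made to rule out neoplastic, infectious, metabolic, toxin, or other etiologic causes prior to labeling an adverse event an irAE".

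**Tabulation (SAP 8.6.2).** The primary irAE analysis uses events that investigators reported as irAEs. An exploratory analysis applies a sponsor definition: "If an AE falls within any of the cluster terms listed below, it will be considered as an irAE". A further table reports treatment-emergent events, up to 90 days after the last dose, for clusters described as immune-mediated; that sentence carries no exploratory label. The Hepatitis cluster begins "acute hepatic failure, autoimmune hepatitis, hepatic failure, hepatitis" and also contains liver injury. Encephalopathy is in the cluster of other immune-related events. For each cluster the SAP reports incidence, severity grade, the percentages treated with corticosteroids or hormones, held, discontinued and resolved, time to onset and duration.

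**The concern.** The protocol defines an irAE partly by exclusion of other causes. The SAP's sponsor definition and cluster table drop that part and match on the preferred term. In a population with advanced cancer, including about 20 subjects with HCC, some listed terms also describe what tumour progression or cirrhosis does. An event that the investigator judged unrelated would still be counted under an immune-mediated title.

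The cluster table is likely to be read as a description of the immune toxicity of an anti-CTLA-4 antibody. With few subjects, one or two misassigned events move a row visibly. Liver failure from progression is also likely to be high-grade, unresolved and not treated with steroids, so it can alter several figures in that row. The investigator-reported and term-based irAE results could then differ for a reason that has nothing to do with the drug, and nothing in the cluster table would show why.

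**Working it through.** The plan states no AE rate, and its sample sizes are expressly non-inferential, so there is no figure of the plan's own to reproduce. The check traces the text and then gives the scale.

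**1. Can progression enter AE data under a term other than progression?** Yes, if it is serious or fatal (Protocol 5.11). The choice of term is left to the site. The section's one example, brain metastases, is in no SAP cluster. So the route to a listed term is possible but not forced.

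**2. Does the SAP select on anything besides the term?** The sponsor definition and the clusters require a listed preferred term and onset within the extended on-treatment period (SAP 6.4). No relationship, investigator irAE status or cause is required.

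**3. Does any other rule remove such an event?** None was found in either document. The one restriction inside the list is on the Diabetes cluster, limited to subjects without prior history. The Hepatitis cluster has no counterpart.

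**4. Is the overlap plausible?** HCC subjects may enter with Child-Pugh A or B7, AST/ALT up to 5 × ULN, and active hepatitis B (on effective antiviral therapy) or C (Protocol 3.2.1, 3.2.2). Protocol 4.1.2 itself names encephalopathy as a sign of hepatic decompensation in these subjects.

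**5. Size per event.** Inputs: up to 60 Phase 2 subjects, about 20 of them with HCC (SAP 3.2). With *m* misassigned subjects and no true immune events, the cluster rate is 100 × *m*/*n*. Wilson 95% limits, with p = m/n and z = 1.96, are [p + z²/2n ± z√(p(1−p)/n + z²/4n²)] / (1 + z²/n). The SAP plans Wilson intervals for efficacy only; they are used here for scale.

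| m | n = 60 | n = 20 |
|---|---|---|
| 0 | 0% (0.0–6.0) | 0% (0.0–16.1) |
| 1 | 1.7% (0.3–8.9) | 5.0% (0.9–23.6) |
| 2 | 3.3% (0.9–11.4) | 10.0% (2.8–30.1) |
| 3 | 5.0% (1.7–13.7) | 15.0% (5.2–36.0) |

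**6. How likely is at least one?** The documents give no rate, so this is an assumed range. Let *r* be the proportion of 20 HCC subjects who have serious liver failure from progression in the window, coded to a listed term. P(at least one) = 1 − (1 − r)²⁰:

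- r = 5%: 1 expected, 64.2%
- r = 10%: 2 expected, 87.8%
- r = 20%: 4 expected, 98.8%

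**7. Other figures in the row.** If *k* true immune events all resolve and *m* misassigned events do not, the percentage resolved is 100 × k/(k + m). Taking k = 2 and m = 1 as an illustration, it falls from 100% to 2/3 = 67%. The percentage given corticosteroids falls in the same way if the misassigned event was not so treated.

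**The case against.** The strongest reply is that the plan already holds the safeguard. The primary irAE analysis is investigator-based, and investigators are told to look for other causes first. The sponsor definition is labelled exploratory. Other tables break TEAEs and serious TEAEs down by relationship, so a reader could find out whether a hepatic failure was judged related. A term search across all causalities also has a purpose: it does not depend on attribution by investigators in an open-label study. All of this stands. It limits the problem to the sponsor-defined summary and the cluster table, and it is a good reason not to remove the all-causality count. It does not help a reader of the cluster table itself, which shows no relationship split.

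Four stronger readings may tempt a reader, and the documents do not support them.

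- *Protocol 5.11 forces organ-specific terms.* It asks for a specific term fitting the diagnosis, and its example names the tumour spread.
- *Neurological toxicity rates are inflated in a table of their own.* There is no neurological cluster; encephalopathy sits in a mixed group.
- *Deaths from progression are hidden among fatal AEs.* Protocol 6.4.1 does plan AE deaths, "together with the number and percentage of subjects who die due to an AE", and the SAP lists "TEAEs leading to death by PT". But the SAP also tabulates drug-related TEAEs leading to death, summarises deaths by reason, and lists the precipitating AE and cause of each death.
- *The HCC cohort will show a 5-point error per event.* The SAP's HCC subgroup sentence follows the overall TEAE summary, and no cluster table by HCC status is clearly planned. The 1.7-point figure is the safer one.

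**Conclusion.** The point holds within limits. The SAP's sponsor-defined irAEs and immune-mediated clusters depart from the protocol's irAE definition by ignoring relationship and cause, and nothing in either document takes out an event judged unrelated. Liver failure or encephalopathy due to tumour or liver disease can therefore be counted as immune-mediated; whether it is depends on the term the site chooses and how it is coded.

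Each such subject adds about 1.7 percentage points over 60 Phase 2 subjects, or 5.0 points if clusters are shown for 20 HCC subjects alone. How many there would be is unknown; the 5% to 20% range above is assumed. The effect on the severity, resolution and steroid figures also assumes that these events tend to be severe, unresolved and not steroid-treated. The origin is the SAP's cluster rule; Protocol 5.11 only supplies events to it. The primary irAE tables and the drug-related TEAE tables are not affected.

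**What to change.** In SAP 8.6.2, keep the all-causality counts for the clusters and for sponsor-defined irAEs. Beside them add a column limited to events rated possible, probable or highly probable/definite, with unresolved causality counted as related, as the SAP already provides. Give the severity, treatment, resolution and timing summaries for both columns.

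Relationship is already collected on the eCRF, so the cost is a sentence or two in the SAP and one column per table. The downside is small: the added column rests on open-label investigator attribution, and an event rated related is not thereby shown to be immune. That is why the all-causality count should stay next to it and not be replaced.
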